5.2.1.2. Supply, Packaging, and Labeling

Ruxolitinib will be supplied as 5 mg tablets packaged in 60-count high-density polyethylene bottles. All tablet excipients comply with the requirements of the applicable compendial monographs.

All Incyte investigational product labels will be in the local language and will comply with the legal requirements of each country and will state "Caution: New Drug--Limited by Federal (or United States) law to investigational use."

5.2.1.3. Storage

Bottles of ruxolitinib tablets should be stored at room temperature, 15°C to 30°C (59°F to 86°F).

5.2.1.4. Instruction to Subjects for Handling Ruxolitinib

The subject must be instructed in the handling of study drug as follows:

- To store the study drug at room temperature.
- To only remove from the study drug bottle/kit the number of tablets needed at the time of administration.
- Not to remove doses in advance of the next scheduled administration.
- To make every effort to take doses on schedule.
- To report any missed doses.
- To take study drug within 1 hour after completing a meal (morning and evening meal) with a glass of water.
- Not to take another dose if vomiting occurs after taking study drug.
- To keep study drug in a safe place and out of reach of children.
- To bring all used and unused study drug kits to the site at each visit.

5.2.2. Corticosteroids

Either oral prednisone or IV methylprednisolone may be used to begin corticosteroid treatment at the investigator's discretion.

5.2.2.1. Prednisone

5.2.2.1.1. Description

Prednisone is a white to off-white, odorless, crystalline powder. Tablets are typically white in color and contain lactose monohydrate, magnesium stearate, microcrystalline cellulose, pregelatinized starch, and sodium starch glycolate. Commonly available dose strengths include 1 mg, 2.5 mg, 5 mg, 10 mg, 20 mg, and 50 mg tablets.

5.2.2.1.2. Supply, Packaging, and Labeling

Investigators are responsible for ensuring that subjects receive commercially available supplies of prednisone for the duration of the study treatment period. Incyte may provide prednisone where required by applicable law or regulation.

5.2.2.1.3. Storage

Prednisone tablets should be stored in accordance with local prescribing information requirements.

5.2.2.2. Methylprednisolone

5.2.2.2.1. Description

Methylprednisolone sterile powder is an anti-inflammatory glucocorticoid, which contains methylprednisolone sodium succinate as the active ingredient. Methylprednisolone sodium

succinate, USP, is the sodium succinate ester of methylprednisolone, and it occurs as a white or nearly white, odorless hygroscopic, amorphous solid. It is very soluble in water and in alcohol; it is insoluble in chloroform and is very slightly soluble in acetone.

5.2.2.2. Supply, Packaging, and Labeling

Investigators are responsible for ensuring that subjects receive commercially available supplies of methylprednisolone for the duration of the study treatment period. Incyte may provide methylprednisolone where required by applicable law or regulation.

5.2.2.3. Storage

Methylprednisolone (unreconstituted product or solution) should be stored in accordance with local prescribing information.

5.2.2.3. Administration of Corticosteroids

Subjects will receive prednisone 2.5 mg/kg per day orally (PO) or methylprednisolone 2.0 mg/kg per day IV. Subjects who previously began corticosteroid therapy at a different dose may remain on that dose if considered appropriate by the treating physician. Corticosteroids should be tapered as per institutional guidelines at a rate that is commensurate with resolution of GVHD manifestations.

A recommended tapering schedule is provided in Table 1.

Study Days	Dose
Days 1-5	Prednisone 2.5 mg/kg QD PO (or methylprednisolone 2.0 mg/kg per day IV)
Days 6-10	Prednisone 2.0 mg/kg QD PO (or methylprednisolone 1.6 mg/kg per day IV)
Days 11-15	Prednisone 1.5 mg/kg QD PO (or methylprednisolone 1.2 mg/kg per day IV)
Days 16-20	Prednisone 1.0 mg/kg QD PO (or methylprednisolone 0.8 mg/kg per day IV)
Days 21-25	Prednisone 0.5 mg/kg QD PO (or methylprednisolone 0.4 mg/kg per day IV)
Days 26-28	Prednisone 0.25 mg/kg QD PO (or methylprednisolone 0.2 mg/kg per day IV)

 Table 1:
 Recommended Corticosteroid Administration Table, Days 1 Through 28

QD = once daily.

If GVHD flares during the taper of corticosteroids, then the dose may be re-escalated at the investigator's discretion and will not be considered treatment failure, as long as the dose does not exceed the initial starting dose. If the dose required exceeds this threshold, or if the flare is unresponsive to increased corticosteroids, or if multiple flares are observed, then the subject will be considered to have experienced treatment failure.

Corticosteroids may be taken or administered without regard to food except on days when PK samples are drawn; on those days, subjects should be instructed to fast and refrain from taking corticosteroids until after PK samples are collected. See Section 7.7.1 for additional information.

5.2.2.4. Prophylactic and Supportive Care Medications

Patients who undergo allo-HSCT are at risk for a variety of infections based on the degree of immunosuppression induced by the conditioning regimen before transplant. As such, it is considered routine practice to use antibiotics, anti-infectives, and immunizations as prophylactic therapies (Tomblyn et al 2009). In cases where post-transplant anti-infective prophylaxis measures are necessary, ongoing therapy may continue at the investigator's discretion per institutional guidelines.

Systemic and topical GVHD prophylaxis medications (eg, cyclosporine, methotrexate, tacrolimus) may be continued at therapeutic doses as appropriate based on stage and sites of disease.

Additional supportive care measures (eg, use of antimotility agents for diarrhea management) are permitted at the investigator's discretion.

5.3. Treatment Compliance

Compliance with all study-related medications should be emphasized to the subject by the site personnel, and appropriate steps should be taken to optimize compliance during the study. Compliance with ruxolitinib will be calculated by the sponsor based on the drug accountability documented by the site staff and monitored by the sponsor/designee (tablet counts). Subjects will be instructed to bring all study-related medications with them to the study visits in order for site personnel to conduct tablet counts to assess study drug accountability. The drug accountability documentation will be used by the sponsor to calculate treatment compliance.

Although commercial supplies of corticosteroids will be used, dose changes and interruptions will also be documented in the medical record and monitored by the sponsor or its designee. As corticosteroid dose strengths and administration types will vary, compliance with corticosteroids will not be calculated.

5.4. Treatment Interruptions and Adjustments

5.4.1. Dose Modifications

Dose interruptions and modifications may occur for individual study subjects based on the presence or absence of toxicity.

5.4.2. Criteria and Procedures for Dose Interruptions and Adjustments of Ruxolitinib

5.4.2.1. Dose Interruptions and Reductions

5.4.2.1.1. Toxicity Management

Treatment with ruxolitinib may be delayed up to 14 days to allow for resolution of toxicity (Table 2). Subjects may resume treatment if no medical condition or other circumstance exists that, in the opinion of the investigator, would make the subject unsuitable for further participation in the study. The investigator should contact the sponsor medical monitor to discuss cases where treatment has been delayed for more than 14 days before restarting treatment.

Because subjects may enter the study with compromised bone marrow function, these dose reductions are provided as guidelines; individual decisions regarding dose reduction should be made using clinical judgment and in consultation with the sponsor's medical monitor, taking into account relatedness of the AE to the study drug and the subject's underlying condition. Adverse events that have a clear alternative explanation or transient (\leq 72 hours) abnormal laboratory values without associated clinically significant signs or symptoms may be exempt from dose-reduction rules.

Subjects who are currently receiving ruxolitinib 10 mg BID may be reduced to 5 mg BID; subjects receiving 5 mg BID may be reduced further to 5 mg QD. Subjects who are unable to tolerate ruxolitinib at a dose of 5 mg QD should be withdrawn from study treatment (Table 3).

ADVERSE EVENT	ACTION TAKEN			
Chemistry				
• AST and/or ALT > 3.0 × ULN in subjects with normal ALT/AST at baseline.	 Step 1: Interrupt study treatment up to 14 days until the toxicity has resolved to ≤ Grade 1. Exceptions require sponsor approval. Step 2: Restart study treatment at same dose. If assessed as related to study treatment, restart study treatment at next lower dose and monitor as clinically indicated. NOTE: In subjects with GVHD-related chemistry elevations at baseline, contact the sponsor medical monitor to discuss clinical management and possible dose reductions. 			
• Total bilirubin elevations that occur in the presence of GVHD response that, in the investigator's opinion, cannot be attributed to new liver GVHD or concomitant therapy.	 Total bilirubin 3.0-5.0 × ULN: Repeat assessment within 7 days. If elevation persists: Reduce ruxolitinib dose by 1 level until bilirubin ≤ 1.5 × ULN. Resume previous dose if resolved in 14 days; if > 14 days, maintain reduced dose. Total bilirubin >5.0-10.0 × ULN: Repeat assessment within 7 days. If elevation persists: Hold ruxolitinib until bilirubin ≤ 1.5 × ULN. Monitor LFTs weekly or more frequently as appropriate. Resume previous dose if resolved in 14 days; if > 14 days, resume at reduced dose. Total bilirubin > 10.0 × ULN: Repeat assessment within 7 days. If elevation persists: Hold ruxolitinib until bilirubin ≤ 1.5 × ULN. Resume at reduced dose. 			
• Total bilirubin elevations that occur in subjects with Stage 1/2 liver GVHD that, in the investigator's opinion, cannot be attributed to worsening liver GVHD or concomitant therapy.	 Total bilirubin > 3.0 × ULN: Repeat assessment within 7 days. If elevation persists: Reduce ruxolitinib dose by 1 dose level. If bilirubin ≤ 3.0 × ULN, may resume previous dose. 			

 Table 2:
 Guidelines for Interruption and Restarting of Ruxolitinib
Table 2: Guidelines for Interruption and Restarting of Ruxolitinib (Continued)

ADVERSE EVENT	ACTION TAKEN
Hematology	•
• ANC < 1.0 × 10 ⁹ /L, suspected as unrelated to study treatment (eg, GVHD, active CMV viremia).	Step 1: Reduce dose of ruxolitinib by 1 dose level. Step 2: Monitor ANC count as clinically indicated. Step 3: If ANC count is $\geq 1.0 \times 10^9$ /L for more than 7 days, then the previous dose of ruxolitinib may be resumed.
 ANC < 1.0 × 10⁹/L, suspected as related to study treatment. ANC < 1.0 × 10⁹/L, with an oral temperature of at least 38.5°C OR with ≥ Grade 3 infection. ANC < 0.5 × 10⁹/L. 	Step 1: Interrupt study treatment for up to 14 days. Step 2: Monitor ANC count as clinically indicated. Step 3: If ANC count is $\geq 1.0 \times 10^9$ /L for more than 7 days, then ruxolitinib may be restarted at 1 dose level below the current dose. Step 4: If ANC count is $\geq 1.0 \times 10^9$ /L for more than 7 days after treatment at a reduced dose, the previous dose level of ruxolitinib may be resumed.

5.4.2.1.2. Coadministration With Strong CYP3A4 Inhibitors or Dual CYP2C9/CYP3A4 Inhibitors

Ruxolitinib is mainly eliminated in humans by oxidative metabolism catalyzed predominantly by cytochrome P450 (CYP) 3A4 and CYP2C9 and is not a substrate for transporters including P-glycoprotein (P-gp). Therefore, concomitant medications that inhibit CYP3A4 and CYP2C9 enzymes might increase exposure to ruxolitinib. See Section 5.6 for additional details.

5.4.2.2. Dose Escalation of Ruxolitinib

Subjects will begin treatment at ruxolitinib 5 mg BID; if hematologic parameters are stable and no treatment-related toxicity is observed after the first 3 days of treatment, the dose may be increased to 10 mg BID. Stable hematologic parameters are defined as the absence of $a \ge 50\%$ decrease in platelet counts and/or ANC relative to Day 1.

As described in Table 2, subjects who have had a dose reduction of ruxolitinib in order to manage toxicity may resume treatment at the previous dose if hematologic parameters meet the required threshold(s).

Subjects who have previously had a reduction in the dose of ruxolitinib may have their dose re-escalated if a GVHD flare is experienced, provided that hematologic thresholds are described in Table 2 are met. Dose re-escalation levels of ruxolitinib are described in Table 4.

Dose increases may not exceed 10 mg BID.

Table 4:	Dose Escalation Levels for Ruxolitinib
----------	---

Current Dose	First Dose Escalation	Second Dose Escalation
5 mg QD	5 mg BID	10 mg BID
5 mg BID	10 mg BID	_

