 - Cholestatic disorders or unresolved veno-occlusive disease of the liver (defined as persistent bilirubin abnormalities not attributable to GVHD and ongoing organ dysfunction).
 - Clinically significant or uncontrolled cardiac disease, including unstable angina, acute myocardial infarction within 6 months from Day 1 of study drug administration, New York Heart Association Class III or IV congestive heart failure, circulatory collapse requiring vasopressor or inotropic support, or arrhythmia that requires therapy.
 - Clinically significant respiratory disease that requires mechanical ventilation support or 50% oxygen.
- Currently breast feeding.
- Received Janus kinase (JAK) inhibitor therapy after allo-HSCT for any indication. Treatment with a JAK inhibitor before allo-HSCT is permitted.
- Treatment with any other investigational agent, device, or procedure, within 21 days (or 5 half-lives, whichever is greater) of enrollment. Subjects participating in a GVHD prophylaxis study or conditioning regimen should be discussed with the sponsor's medical monitor before enrollment.
- Any condition that would, in the investigator's judgment, interfere with full participation in the study, including administration of study drug and attending required study visits; pose a significant risk to the subject; or interfere with interpretation of study data.
- Known allergies, hypersensitivity, or intolerance to any of the study medications, excipients, or similar compounds.

Study Drug, Dosage, and Mode of Administration:

Subjects will begin treatment at ruxolitinib 5 mg BID; the dose may be escalated to 10 mg BID after 3 days if hematologic parameters are stable and no treatment-related toxicity is observed. Subjects may have dose reductions during the course of treatment based on safety and laboratory assessments. The dose of ruxolitinib may be re-escalated if toxicity management thresholds are met or if a subject experiences a GVHD flare and has adequate hematologic parameters. The dose of ruxolitinib may not exceed 10 mg BID. Tapering of ruxolitinib is permitted provided the subject has reached the Day 180 visit, achieved a CR or VGPR, and discontinued corticosteroid therapy for at least 8 weeks.

Reference Therapy, Dosage, and Mode of Administration:

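### The flare rule for ruxolitinib re-escalation sets only blood-count conditions, so it can restore the earlier dose while a bilirubin elevation that Table 2 says must first recover is still unresolved

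*Protocol*

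**What the plan says.** **Flare rule.** Protocol 5.4.2.2, third paragraph, covers any subject with an earlier ruxolitinib reduction. The dose may be "re-escalated if a GVHD flare is experienced, provided that hematologic thresholds are described in Table 2 are met". The synopsis (Study Drug, Dosage, and Mode of Administration) allows re-escalation "if toxicity management thresholds are met or if a subject experiences a GVHD flare and has adequate hematologic parameters".

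**Table 2 (5.4.2.1.1), GVHD-response row.** For bilirubin, this row covers "elevations that occur in the presence of GVHD response that, in the investigator's opinion, cannot be attributed to new liver GVHD or concomitant therapy". In its 3.0-5.0 × ULN tier, if the elevation persists on repeat testing, the instruction is "Reduce ruxolitinib dose by 1 level until bilirubin ≤ 1.5 × ULN", and then "Resume previous dose if resolved in 14 days; if > 14 days, maintain reduced dose".

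**Table 2, Stage 1/2 liver GVHD row.** This covers elevations which "occur in subjects with Stage 1/2 liver GVHD that, in the investigator's opinion, cannot be attributed to worsening liver GVHD or concomitant therapy". If bilirubin above 3.0 × ULN persists on repeat, the instruction is "Reduce ruxolitinib dose by 1 dose level. If bilirubin ≤ 3.0 × ULN, may resume previous dose".

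**First increase to 10 mg BID.** Under the first paragraph of 5.4.2.2, the step up after 3 days needs two things: stable hematology and no treatment-related toxicity.

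**The concern.** The flare rule and Table 2 can give different answers for the same subject. Where the reduction was made for bilirubin, Table 2 asks whether bilirubin has recovered, while 5.4.2.2 asks only about blood counts. The two rows are reserved for elevations that the investigator cannot put down to new or worsening liver GVHD or to concomitant therapy, and the prescribed response is less ruxolitinib. A site relying on 5.4.2.2 could reverse that response while its reason persists. The condition on the first increase makes this look like an omission: the flare route can restore the same 10 mg BID but drops the toxicity half of the test, for subjects who have already needed a reduction. At stake are dosing safety and consistency across about 40 sites. No statistical quantity in the plan changes.

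**Working it through.** The plan states no figure to reproduce. The check compares the texts and adds simple dose arithmetic.

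**1. Can the toxicity thresholds be read into the flare rule?** The synopsis joins the two routes with *or*, so the flare route stands apart from them. In 5.4.2.2 the second paragraph points to Table 2 generally for resuming a dose after toxicity, although it too names only hematologic parameters. The third paragraph cites Table 2 for hematologic thresholds only.

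**2. Which non-hematologic entries in Table 2 leave a subject on a reduced dose with the toxicity unresolved?**

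| Entry | Action | Recovery required first? | Conflict with flare rule |
|---|---|---|---|
| AST/ALT > 3.0 × ULN | Interrupt | Yes, to ≤ Grade 1 | No |
| Bilirubin 3.0-5.0 × ULN, GVHD-response row | Reduce 1 level | No; return tied to ≤ 1.5 × ULN | Arguable |
| Bilirubin > 5.0 × ULN tiers, same row | Hold | Yes, to ≤ 1.5 × ULN | No |
| Bilirubin > 3.0 × ULN, Stage 1/2 liver GVHD row | Reduce 1 level | No; return tied to ≤ 3.0 × ULN | Clear |
| Other Grade 3 toxicity | Interrupt | Yes, to ≤ Grade 1 | No |

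Two entries remain. The first is only arguable because its scope depends on GVHD responding. One reading is that this describes when the elevation arose, so the recovery condition continues. Another is that a flare ends the response and the row stops governing. The Stage 1/2 row has no such qualifier.

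**3. An example in the clear row (values assumed for illustration).** A subject with Stage 1/2 liver GVHD on 10 mg BID has persistent bilirubin of 4 × ULN, not attributed to worsening liver GVHD or concomitant therapy, and is cut to 5 mg BID. The skin then flares, counts are adequate, and bilirubin is still 4 × ULN. Table 2 withholds the previous dose because 4 > 3.0. Section 5.4.2.2 permits 10 mg BID.

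**4. Dose change (Tables 3 and 4).** Daily doses are 5 mg QD = 5 mg, 5 mg BID = 10 mg and 10 mg BID = 20 mg. A one-level return is 20/10 = 2.0 or 10/5 = 2.0. Each restores the pre-reduction dose, within the 10 mg BID cap.

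**5. Distance from recovery.** In the 3.0-5.0 × ULN tier, the elevation is 3.0/1.5 = 2.0 to 5.0/1.5 = 3.3 times the recovery level. The Stage 1/2 row gives no upper limit, so its ratio is simply above 1.

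**6. Monitoring.** Table 6 schedules chemistry every 7 days from Day 7 to Day 56, then every 28 days plus Day 100. The instruction "Monitor LFTs weekly or more frequently as appropriate" appears only in the > 5.0-10.0 × ULN tier. However, Protocol 8.1.1 makes a laboratory abnormality that requires a study-drug change an adverse event. Section 8.1.2 requires reassessment at each visit, or more often if necessary, and 8.2 requires follow-up to normal or an adequate explanation. Section 6.5 allows unscheduled testing. A 28-day interval is therefore a worst case.

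**The case against.** The strongest opposing case is that the text is permissive and apparently deliberate. The flare rule says *may*, Table 2 is offered as guidance subject to clinical judgment, and the *or* in the synopsis shows that a separate flare route was intended. An uncontrolled flare is costly: needing additional systemic therapy forces withdrawal from study treatment (5.5.1). Section 1.4 names reduced hematopoiesis as the primary risk, so blood counts are a sensible main condition. Section 7.6.1 presumes liver GVHD when bilirubin rises with or after GVHD in another organ and no other cause is identified; once an elevation is re-attributed in that way, the rows no longer apply.

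All of this stands as a limit on frequency and seriousness. It supports keeping the blood-count condition and an early flare route. It does not supply the missing bilirubin condition for a subject whose elevation is still not attributed to new or worsening liver GVHD.

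The other safeguards do not supply it either. In 5.4.4 and 5.5.1, the provisions on drug-related toxicity and injury to the subject govern stopping, not dose increases. The 14-day criterion in 5.4.4 needs a delay of therapy, and these two entries involve none. Monitor consultation in 5.4.2.1.1 is worded for reductions and for long delays. The adverse event rules govern follow-up.

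Several stronger inferences are tempting but unsupported:

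- **Sites are told to escalate.** They are only permitted to.
- **Table 2 as a whole is overridden.** The other non-hematologic entries that interrupt or hold the drug require recovery before restart.
- **Subjects go unmonitored for 28 days.** Section 8 requires active follow-up, and applying the rows' own recovery conditions needs interim testing.
- **The dose could rise fourfold.** The step in Table 4 from 5 mg QD to 10 mg BID is a second escalation. The conflict shown here is a one-level return.

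**Conclusion.** The point holds in a narrow form. At a GVHD flare, 5.4.2.2 and the synopsis permit, without requiring, a return to the pre-reduction dose on hematologic criteria alone. This clearly conflicts with the Stage 1/2 liver GVHD row, and arguably with the 3.0-5.0 × ULN tier of the GVHD-response row. The consequence is a doubling of the reduced daily dose, never above 10 mg BID, while an elevation not attributed to new or worsening liver GVHD or to concomitant therapy is unresolved.

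This assumes that the flare is outside the liver, or at least that the elevation is not re-attributed at the flare, and that the site follows 5.4.2.2 as written. Such subjects are probably few, and the documents give no basis for a count. It is a minor patient-safety inconsistency, worth correcting because correction is cheap. The scheduled monitoring interval should not carry the argument.

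**What to change.** In the third paragraph of 5.4.2.2 and in the flare limb of the synopsis, keep the hematologic condition and add:

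*and, where the reduction was for a bilirubin elevation not attributed to new or worsening liver GVHD, bilirubin has recovered to the level in its Table 2 row (≤ 1.5 × ULN or ≤ 3.0 × ULN), or the medical monitor agrees to earlier re-escalation.*

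State also that, at a flare, this replaces the GVHD-response row's rule of keeping the reduced dose when recovery takes more than 14 days, once bilirubin has recovered. Without that sentence the new clause would still disagree with Table 2 for late recoverers. Monitor agreement should not be needed once bilirubin has recovered. Section 5.4.2.3 on tapering can stay as it is.

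The cost is one clause in two places and one clarifying sentence, at the next amendment or in a clarification letter. No procedure is added and no analysis changes. The downside is that an occasional flare re-escalation waits for contact with the monitor.
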